6.2.4. Assessment Window

The assessment time points defined below are used in the analysis. When calculating the assessment date, the visit closest to the specified date is used, and if the period from the specified date is the same, the latest visit is used.

Assessment window will be applied to early withdrawal dates. If participants prematurely withdraw from the study and do not have the visit date of Week 96, 673 days after Week 0 will be imputed to missing visit date of Week 96.

If the derived data based on the study day is included in the range of period, the corresponding week is assigned as below and will be used for analysis.

Assessment time points	Specified data	Window	Period	iod (day)	
Assessment time points	specified date	(±day)	From	to	
Week 0	1	-	-28	1	
Week 12	85	28	57	113	
Week 24	169	28	141	197	
Week 36	253	28	225	281	
Week 48	337	28	309	365	
Week 60	421	28	393	449	
Week 72	505	28	477	533	
Week 84	589	28	561	617	
Week 96	673	28	645	701	

The following shows the assessment window for the follow-up period.

Assessment time noint	Specified data	Window	Period (day)	
Assessment time point	specified date	(±day)	From	to
Follow Week 0	1	-	-	1
Follow Week 12	85	28	57	113
Follow Week 24	169	28	141	197
Follow Week 36	253	28	225	281

Assessment time point	Specified date	Window	Period (day)	
		(±day)	From	to
Follow Week 48	337	28	309	365
Follow Week 60	421	28	393	449
Follow Week 72	505	28	477	533
Follow Week 84	589	28	561	617
Follow Week 96	673	28	645	701

OCS dose and immuno-suppressive therapy is recorded on a daily basis and will be averaged into 12-weekly periods as below. If the date of dose of Nucala at Week 0 is missing, the latest available date between the screening visit date and the Week 0 visit date will be used for the start date of the observation period.

12-weekly period	First date	Last date
Weeks 9-12	Nucala start date at Week 0 +	Nucala start date at Week 0 +
	56 days	84 days
Weeks 21-24	Nucala start date at Week 0 +	Nucala start date at Week 0 +
	140 days	168 days
Weeks 33-36	Nucala start date at Week 0 +	Nucala start date at Week 0 +
	224 days	252 days
Weeks 45-48	Nucala start date at Week 0 +	Nucala start date at Week 0 +
	308 days	336 days
Weeks 57-60	Nucala start date at Week 0 +	Nucala start date at Week 0 +
	392 days	420 days
Weeks 69-72	Nucala start date at Week 0 +	Nucala start date at Week 0 +
	476 days	504 days
Weeks 81-84	start date at Week $0 + 560$	Nucala start date at Week 0 +
	days	588 days
Weeks 93-96	Nucala start date at Week 0 +	Nucala start date at Week 0 +
	644 days	672 days

6.2.6. Handling of Partial Dates

Element	Reporting Detail			
General	• Partial dates v displays.	will be displayed as captured in participant listing		
	• However, where necessary, display programs may impute dates as temporary variables for sorting data in listings only. In addition, partial dates may be imputed for 'slotting' data to study phases or for specific analysis purposes as outlined below.			
	• Imputed partial dates will not be used to derive study day, time to onset or duration (e.g., time to onset or duration of adverse events), or elapsed time variables (e.g., time since diagnosis). In addition, imputed dates are not used for deriving the last contact date in overall survival analysis dataset.			
Adverse Events	• Partial dates f following con	or AE recorded in the eCRF will be imputed using the ventions:		
	Study start date is defined as the date of dose of Nucala at Week 0.			
	Missing start day	If study start date is missing (i.e. participant did not start study), then set start date = 1st of month.		
		Else if study start date is not missing:		
		 If month and year of start date = month and year of study start date, then 		
		• If stop date contains a full date and stop date is earlier than study start		

Element	Reporting Detail		
		date, then set start date= 1st of month.	
		• Else set start date = study start date.	
		Else set start date = 1st of month.	
	Missing start day and month	If study start date is missing (i.e. participant did not start study), then set start date = January 1.	
		Else if study start date is not missing:	
		 If year of start date = year of study start date, then 	
		• If stop date contains a full date and stop date is earlier than study start date, then set start date = January 1.	
		• Else set start date = study start date.	
		Else set start date = January 1.	
	Missing end day	A '28/29/30/31' will be used for the day (dependent on the month and year).	
	Missing end day and month	No Imputation	
	Completely missing start/end date	No imputation	
Concomitant Medications/ Medical History	• Partial dates for will be impute	or any concomitant medications recorded in the CRF ed using the following convention:	
	Missing start day	If study start date is missing (i.e. participant did not start study), then set start date = 1st of month.	
		Else if study start date is not missing:	
		 If month and year of start date = month and year of study start date, then 	
		• If stop date contains a full date and stop date is earlier than study start date, then set start date= 1st of month.	
		• Else set start date = study start date.	
		Else set start date = 1st of month.	

Element	Reporting Detail			
	Missing start day and month	If study start date is missing (i.e. participant did no start study), then set start date = January 1.		
		Else if study start date is not missing:		
		 If year of start date = year of study start date, then 		
		• If stop date contains a full date and stop date is earlier than study start date, then set start date = January 1.		
		• Else set start date = study start date.		
		Else set start date = January 1.		
	Missing end day	A '28/29/30/31' will be used for the day (dependent on the month and year).		
	Missing end day and month	A '31' will be used for the day and 'Dec' will be used for the month.		
	Completely missing start/end date	No imputation		
Age	 Age will be calculated based on the screening visit date. Birth date will be imputed as follows: Any participant with a missing day and month will have this imputed as '30th June'. Birth date will be presented in listings as 'YYYY'. 			

Trademarks

Trademarks of the GlaxoSmithKline Group of Companies

Nucala

Trademarks not owned by the GlaxoSmithKline Group of Companies

SAS

7. **REFERENCES**

GlaxoSmithKline PMS protocol No. 208505 NUCALA Subcutaneous Injection Special Drug Use Investigation (EGPA, Long-term) ver. 3.0. 30-Jul-2019.

Post–marketing Surveillance of Mepolizumab Use in Patients with Eosinophilic Granulomatosis with Polyangiitis in Japan: Interim Analysis. Therapeutic Research vol. 42 no. 6 2021.

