4.3.1.2.5. Average daily dose of OCS and Dosing categories

Endpoints

- Average daily dose (prednisolone-equivalent) of OCS
- The proportion of participants in the dosing categories relative to average daily OCS (prednisolone-equivalent)

Specification

To calculate the dose of OCS by prednisolone equivalent, multiply by the following coefficients.

Generic name	GSK Drug Code	Prednisolone equivalent value	Coefficient
Hydrocortisone	00028601	20	0.250
Hydrocortisone succinate	00028602	20	0.250
Cortisone acetate	00014602	25	0.200
Prednisolone	00016201	5	1.000
Prednisolone succinate	00016203	5	1.000
Methylprednisolone	00049601	4	1.250
Methylprednisolone succinate	00049602	4	1.250
Triamcinolone	00031901	4	1.250
Triamcinolone acetonide	00031902	4	1.250
Dexamethasone	00016001	0.75	6.667
Dexamethasone phosphate	00016002	0.75	6.667
Paramethasone acetate	00066402	2	2.500
Betamethasone	00008501	0.75	6.667
Betamethasone phosphate	00008502	0.75	6.667

Average daily dose of OCS for each participant will be calculated by 12-weekly periods and the retrospective period as:

Total dosage of OCS (mg) / Total duration of administration of OCS (day) Total duration of administration is defined as:

• By 12-weekly period

Last date of each period - later date of (first date of each period or start date of OCS) +1

12-weekly period is described in Section 6.2.4. If OCS is administered and then OCS is no longer required on the last date of each period, 0 mg will be imputed.

• Retrospective period

Last date of retrospective period–later date of (start date of retrospective period or start date of OCS) + 1

Average daily OCS in the retrospective period will be calculated if a participant uses OCS in the retrospective period, otherwise average daily OCS will be 0 mg. If OCS is administered and then OCS is no longer required on the last date of the retrospective period, 0 mg will be imputed.

Over observation period

Last day of observation period (Week 48 for interim analysis, if participant is on-going on observation period) - later date of (date of dose of Nucala at Week 0 or start date of OCS) +1.

If the date of dose of Nucala at Week 0 is missing, the latest available date between the date of screening visit and the date of visit at week 0 will be used for calculation of observation period. If OCS is administered and then OCS is no longer required during the observation period, 0 mg will be imputed.

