6.2.2. Study Period

Assessments and events will be classified according to the time of occurrence relative to the study period.

Screening period is defined as 0-4 weeks before the date of dose of Nucala at Week 0.

Observation period is defined as time from the date of dose of Nucala at Week 0 to the stop date of Nucala +28 days for the participants who did not withdraw from study, or the first treatment discontinuation date +28 days for the participants who withdraw from study. If the date of dose of Nucala at Week 0 is missing, the latest available date between the screening visit date and the Week 0 visit date will be used for the start date of the observation period. When the last Nucala stop date is missing, the last Nucala start date will be imputed.

Follow-up period is defined as time from the first treatment discontinuation date +29 days to 96 weeks within the observation period at maximum. The follow-up period is only applicable for the participants who discontinued the treatment.

Retrospective period is defined as time (within 12 weeks) before the first dose of Nucala. For data of hospitalization for EGPA-related events and ER/Unscheduled visit for EGPA-related events the period is defined as time (within 48 weeks) before the first dose of Nucala.

The study periods to use for summaries on each endpoint are as below.

A:	PMS period	B: Observation period
Retrospective		
period		

Participants who completed the study

Participants who discontinued and moved to the follow-up period

C:	PMS period	D: Observation	E: Follow-up
Retrospective		period	period
period			

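### SAP 6.2.6 reads a missing Week 0 dose date as not having started, so some partially dated AEs of treated participants can be placed before the observation period

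*SAP*

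**What the plan says.** SAP 6.2.6 (Handling of Partial Dates) gives this definition for the AE rows: "Study start date is defined as the date of dose of Nucala at Week 0". No substitute is offered if that date is absent. If it is absent and the AE lacks only its start day, the rule is "If study start date is missing (i.e. participant did not start study), then set start date = 1st of month". If the AE lacks day and month, it is "If study start date is missing (i.e. participant did not start study), then set start date = January 1".

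If study start is known, a partial date in the same month (day missing) or the same year (day and month missing) is handled by "Else set start date = study start date", unless a complete stop date precedes study start. For a missing day in any other month the rule is "Else set start date = 1st of month"; for a missing day and month in any other year it is 1 January. The concomitant-medication rows repeat this logic.

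Elsewhere the SAP handles the same missing date differently. SAP 6.2.2 (Study Period) supplies a substitute for an absent Week 0 dose date: "the latest available date between the screening visit date and the Week 0 visit date will be used for the start date". This fixes where observation begins. SAP 6.2.4 repeats this for the 12-weekly windows. SAP 4.3.1.2.5 does so for average OCS dose, in a clause that opens "If the date of dose of Nucala at Week 0 is missing, the latest available date between the date of screening visit"; its other candidate is the Week 0 visit.

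**The concern.** The same participant can have an observation period under 6.2.2 and count as never having started under 6.2.6. That participant can be in the Treated Population, because SAP 3 asks only for at least one injection, not for a recorded Week 0 dose date.

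This bears on the primary endpoint. SAP 6.2.6 allows imputed dates to be used for assigning data to study phases, 6.2.2 assigns events by when they occurred, and 4.2.2 tabulates AEs, ADRs, SAEs and AESIs for the observation period and for observation plus follow-up. Both periods begin at the start of observation, so an AE dated earlier appears in neither. The known-start branch is built to keep ambiguous AEs in the period; the missing-start branch does the opposite.

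**Working it through.** The documents state no figure on this point, so there is none to reproduce. The check is on the date logic.

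**Inputs.** F is the fallback start of the observation period (6.2.2). The imputation rules are those of 6.2.6. The tabulated periods are those of 4.2.2.

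**Step 1: where the two branches differ.**
- Study start missing, as written: imputed start is the 1st of the month, or 1 January.
- Study start set to F: imputed start is F if the AE is in the same month (day missing) or same year (day and month missing) as F and no complete stop date precedes F. Otherwise it is the 1st of the month or 1 January.

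The results therefore differ only in that same month or year, and not if F is itself the 1st of the month or 1 January respectively.

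**Step 2: example.** F = 15 June 2021, AE ongoing.

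| AE start as recorded | 6.2.6 as written | With F as study start |
|---|---|---|
| 2021 | 1 Jan 2021, before the period | 15 June 2021, inside |
| June 2021 | 1 June 2021, before the period | 15 June 2021, inside |
| July 2021 | 1 July 2021, inside | 1 July 2021, inside |
| 2022 | 1 Jan 2022, inside | 1 Jan 2022, inside |

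Distance for the first row: 31 + 28 + 31 + 30 + 31 + 14 = 165 days. For the second: 15 − 1 = 14 days.

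**Step 3: share of partially dated AEs affected, given a missing Week 0 dose date.** Two assumptions are not in the documents: true onset is uniform over a 673-day observation period, and F is uniform over a 365-day calendar year.
- Day and month missing: the days at risk are those from F to 31 December, or none if F is 1 January. Their mean is (364 × 365 / 2) / 365 = 182, and 182 / 673 = 27%. The range is 0 to 364 / 673 = 54%.
- Day missing: the days at risk are those from F to the end of its month, or none if F is the 1st. A month of n days contributes n(n − 1)/2 in total. Over the year this is 7 × 465 + 4 × 435 + 378 = 5373. The mean is 5373 / 365 = 14.7 days, and 14.7 / 673 = 2.2%. The range is 0 to 30 / 673 = 4.5%.
- For a 337-day period (the Week 48 interim) the means are 54% and 4.4%. For 701 days they are 26% and 2.1%.
- With F as study start the share is 0% in every case, leaving aside the stop-date exception.

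These are shares of an unknown, probably small, number of records.

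**The case against.** The strongest reply is that the remark in brackets in 6.2.6 limits the branch to participants who truly never started, so a starter with an unrecorded dose date is not sent to the wrong rule. That reading is possible. But the only alternative branch requires a study start date that is not missing, so such a participant would then have no rule at all. Either way 6.2.6 needs the fallback.

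Other points stand in part. The fallback clauses are conditional, and no document reports a participant with a missing Week 0 dose date. Imputation for phase assignment is permitted rather than required. All AEs are listed (SAP 4.2.2), with partial dates shown as captured, so nothing is hidden.

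A reader might infer more than the documents support:
- *That all partially dated AEs of these participants are moved.* Step 1 shows that only those in the same month or year as the fallback start can be.
- *That every such shift removes a true observation-period event.* AEs are collected from consent (Protocol 6.2.1), and screening can run up to 4 weeks before Week 0 (Protocol 9.1). An AE dated June 2021 may really have begun in screening, and the 1st of the month would then give the right period. Step 3 leaves this case out by assumption.
- *That exposure-adjusted rates lose the event but keep the time.* SAP 6.2.3 has a fallback only for a missing stop date, so the documents do not show what exposure is used when the start date is missing.
- *That relapse events are lost through the medication rows.* Under SAP 4.3.1.2.2 a dose increase counts from the day after the Week 0 visit and an initiation only after the Nucala start date. A record moved to the fallback start, normally the Week 0 visit date, would generally not count either. SAP 6.1.4 also places a partially dated medication in every period in which it could have been taken.

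**Conclusion.** The inconsistency is real and minor. Followed as written, 6.2.6 can place an AE of a treated participant before the observation period and out of the primary AE tables, where the same AE with a known dose date would be counted. This requires three things together: a missing Week 0 dose date, a partial AE start date in the same month or year as the fallback start, and no complete stop date before that start. Where the branches differ, the current wording always gives the earlier date. The absolute effect cannot be computed, because neither the number of missing Week 0 dose dates nor the number of partial AE dates is given. The percentages in the working rest on assumed uniform onset and start dates and show only which kind of partial date is most exposed.

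**What to change.** In SAP 6.2.6, define study start date as the start of the observation period under 6.2.2: the Week 0 dose date or, if that is missing, the latest available of the screening and Week 0 visit dates. Apply the non-starter branch only to participants who received no Nucala injection in the study and so have no observation period. Absence of a Week 0 dose would be the wrong criterion, since the Treated Population needs any one injection. Use the same definition in the concomitant-medication rows for consistency.

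This gives participants with a missing dose date the same convention as everyone else, including its tendency to count ambiguous start-month AEs in the observation period. It costs one sentence in the SAP and one shared derived variable, with no new data.
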